7.1. Inclusion Criteria

Patients are eligible to be entered and enrolled in the study only if they meet **all** of the following criteria:

- [1] Histologically confirmed diagnosis of relapsed intracranial GB (WHO Grade IV; including gliosarcomas). Patients may be entered based on local pathology from the original diagnostic tumor specimen.
Patients who have secondary GBs will also be eligible for this trial.
To confirm the original diagnosis for all patients, the original diagnostic tumor specimen must be made available for a central pathology review (this will be returned to the original pathology laboratory).
- [2] Patients must have evidence of tumor progression as determined by RANO criteria (see [Attachment 5](#)) following standard chemoradiation (Stupp protocol).
 - Magnetic resonance imaging (MRI) must be performed within 14 days prior to enrollment, and patients who are receiving steroids must be stable for at least 5 days prior to imaging. If the steroid dose is increased between the date of imaging and enrollment, a new baseline MRI is required. An MRI must be used throughout the period of study treatment for tumor measurement.
 - Patients must have completed only 1 prior course of radiation therapy and must have experienced an interval of ≥ 12 weeks from the completion of radiation therapy to study entry.

- Patients may have received 1 prior TMZ-based chemotherapy regimen: chemotherapy treatment with concurrent radiotherapy or chemotherapy treatment in the adjuvant setting will each be considered 1 regimen.
- Patients must have experienced an interval of no less than 30 days from the last day of receiving a chemotherapy treatment prior to receiving study therapy (for biologics and targeted agents for at least 14 days) or shorter depending on their known PK plasma half-life).

[3] Patients may have undergone prior surgical resection and will be eligible if the following conditions apply:

- Patients must have recovered from the effects of surgery.
- Evaluable or measurable disease must be present (RANO criteria). To adequately assess the extent of residual disease postoperatively, MRI should be done:
 - In the immediate postoperative period (<72 hours).
Note: if the 72-hour scan is performed more than 14 days prior to enrollment, the scan needs to be repeated. An optimal baseline scan is done 48 hours after surgery.

OR

- In the postoperative period (>4 weeks postoperatively and <14 days of enrollment). For patients receiving steroids, they must be on stable treatment for at least 5 days.
Note: If the steroid dose is increased between the date of imaging and enrollment, a new baseline MRI is required on a stable steroid dosage of at least 5 days duration.

[4] Have available tumor tissue (mandatory) for additional prognostic and predictive biomarker evaluation (from initial pathological diagnosis tissue and/or from subsequent tumor tissues).

[5] Have a performance status (PS) of 0 or 1 on the Eastern Cooperative Oncology Group (ECOG) scale. See [Attachment 4](#).

[6] Have discontinued all previous treatments for cancer excluding palliative treatments and recovered from the acute effects of therapy (given the toxicity profile, mitomycin-C has to be discontinued at least 42 days and all other chemotherapies 30 days from last administration or for biologics and targeted agents for at least 14 days), or shorter depending on their known PK plasma half-life.

At the discretion of the investigator, hormone-refractory prostate cancer patients who are stable on gonadotropin-releasing hormone (GnRH) agonist therapy and breast cancer patients who are stable on antiestrogen therapy (for example, an aromatase inhibitor) may have that treatment continued while they are enrolled in this study.

[7] Have adequate organ function, including:

- Adequate bone marrow reserve: absolute neutrophil count (ANC) $\geq 1.5 \times 10^9/L$, platelet count $\geq 100 \times 10^9/L$, and hemoglobin $\geq 9 \text{ g/dL}$ (6.21 mmol/L).
- Hepatic: total bilirubin $\leq 2 \times$ the upper limit of normal (ULN); alkaline phosphatase (ALP), aspartate aminotransferase (AST), and alanine aminotransferase (ALT) $\leq 3 \times$ ULN.
- Renal: serum creatinine $< 1.5 \times$ ULN.
- Eligibility for hemoglobin may be reached by transfusion. Patients with hemoglobin $> 8 \text{ g/dL}$ but $< 9 \text{ g/dL}$ may receive erythrocyte transfusions to achieve a hemoglobin level $\geq 9 \text{ g/dL}$. Initial treatment must not begin until 2 days after the erythrocyte transfusion and after the confirmation of hemoglobin level $\geq 9 \text{ g/dL}$.
- Note: Small changes from the outlined laboratory values, which are a result of biological or laboratory equipment variability as evidenced by historical values, will be deemed as consistent with the protocol-requirements provided that they are isolated values, are transient, and are not reflective of a medical condition. Repeat laboratory/hematological tests should be done prior to dosing the patient on Cycle 1 Day 1.

[8] Are males or females at least 18 years old at the time of screening.

[8a] Male patients:

- agree to use a reliable method of birth control during the study and for at least 12 weeks following last dose of study drug or country requirements, whichever is longer.

[8b] Female patients:

- are women of child-bearing potential who test negative for pregnancy at the time of enrollment based on a urine pregnancy test and agree to use a reliable method of birth control during the study and for 3 months following the last dose of the investigational product.
- are postmenopausal women, defined as:
 - at least 6 weeks post surgical bilateral oophorectomy with or without hysterectomy, confirmed by medical history.

OR

- spontaneous amenorrhea for at least 12 months, not induced by a medical condition such as anorexia nervosa and not taking medications during the amenorrhea that induced the amenorrhea (for example, oral contraceptives, hormones, gonadotropin releasing hormone, antiestrogens, selective estrogen receptor modulators, or chemotherapy).

OR

- spontaneous amenorrhea 6 to 12 months and a follicle-stimulating hormone (FSH) level greater than 40 mIU/mL.

- [9] Have given written informed consent/assent prior to any study-specific procedures.
- [10] Are able to swallow capsules (lomustine) and tablets (LY2157299/placebo).

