10.4.1. Samples for Standard Safety Laboratory Testing

Standard laboratory tests, including chemistry, hematology, and urinalysis panels will be performed.

[Attachment 2](#) lists the specific tests that will be performed for this study. For all women with reproductive potential, a serum or urine pregnancy test will be performed at the investigative site or at a local laboratory to determine the patient's eligibility. In addition, a serum pregnancy test will be done at a central laboratory and may be used instead of a local laboratory evaluation.

Blood and urine samples will be collected at the times specified in the Study Schedule ([Attachment 1](#)).

Blood serum and plasma will be collected by venipuncture or through a central line.

Cerebrospinal fluid may be collected by lumbar puncture. It is estimated that per CSF assessment, approximately 100 μ l are needed. See [Attachment 3](#) for sample collection times.

To confirm the original diagnosis for all patients, the original diagnostic tumor specimen must be made available for a central pathology review. This will be returned to the original pathology laboratory.

A small amount of preserved tissue previously taken to diagnose the patient's disease (diagnostic pathological tumor tissue/slides and if available, subsequent tumor tissue/slide) will be obtained for evaluating the TGF- β -associated pathways and the GB subsets. This will include genetic, protein, or biochemical research. If both (initial diagnostic tissue and subsequent tissue) are available, both should be provided. The tissue is currently preserved in wax and will be sent to specific laboratories. Tissue block or 10 slides (minimum of 9 slides) is needed. Tissue/slides obtained for this purpose will not be returned to the site after testing. Patients who do not have adequate tissue for the PD part will be allowed to continue in the study.

Routine laboratory tests will be analyzed by a central laboratory selected by Lilly. Patients may be enrolled on local laboratory values only.

Other clinical laboratory tests, which are specialized for safety and efficacy, will be analyzed by a central laboratory.

Laboratory or analyte results that could unblind the study will not be reported to investigative sites or other blinded personnel until the study has been unblinded.

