6.13.4. Clinical Laboratory Evaluation

Listings of all laboratory results will be provided (using SI units [International System of Units], when available) by treatment, separately for hematology, chemistry, urinalysis, special chemistry, ECG chemistry, immune phenotype, whole blood for Fox3p, and urine C-terminal telopeptides of Type 1 collagen. Normal reference ranges, percent of the result outside of range (result divided by lower limit if result is less than lower limit; result divided by higher limit if result is greater than higher limit) and percent change from baseline will also be included.

A calculated CTCAE grade using CTCAE version 4 will be provided for all laboratory results which can be used independently of clinical judgment to determine a CTCAE severity grade. These summaries will be repeated for abnormal laboratory results.

The CTCAE term will be summarized by CTCAE grade in separate tables, linking these AEs to the laboratory term.

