6.15. Protocol Violations

Protocol violations will be identified based on information recorded on the investigator log and through statistical programming of the data. A list of data dependent protocol violations in general and specific to this study is as follows:

General:

- Not meeting protocol inclusion/exclusion criteria [2], [3], [5] to [9], [11], [13] to [17]
- If patient with “entry criteria not met” is marked at screening (visit 0) but patient moves on to cycle 1
- Use of prohibited concomitant therapy (See Protocol Section 9.7):
 - Chemotherapy;
 - Radiation therapy;
 - Immunotherapy;
 - Cancer-related hormonal therapy;
 - Surgery for cancer;
 - Experimental/investigational medication;

- Routine use of granulocyte colony-stimulating factors. They may be used for patients who have ANC $\leq 0.5 \times 10^9/L$, neutropenic fever, or documented infections at investigator's discretion, but cannot be used during Visit 0 to meet hematological inclusion criteria and must be discontinued at least 24 hours prior to the start of therapy.
- Any disease progression requiring other forms of specific anti-tumor therapy will be cause for early discontinuation from the study.
- Treatment compliance with LY2157299 is less than **CCI**% of the prescribed/intended amount of drug per cycle
- Incorrect dose administered (e.g., more than intended)
- Informed consent violations, including patients that have had cerebral spinal fluid (CSF) collected but informed consent for CSF not signed

Study specific:

- Visit outside visit intervals specified in protocol:
 - lomustine therapy is held for ≥ 12 weeks from the last dose of lomustine due to any reason and the patient is not discontinued from the study
- If the patient had two prior dose reductions in lomustine therapy and needs a third reduction due to toxicities but is not discontinued from lomustine therapy
- Failure to perform PK collections
 - only collections "not done" are considered significant protocol violations.
- Failure to collect samples of tumor tissue (at screening only)
- Failure to perform safety procedures or missing safety measurements per requirements in Study Schedule (Attachment 1 in Protocol)
 - Hematology/chemistry
 - ECG
 - ECHO

Note: only collections "not done" are considered significant protocol violations.

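### The hemoglobin entry limit in inclusion criterion [7] is printed in two units that do not agree: 9 g/dL and 6.21 mmol/L are about 1 g/dL apart

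*Protocol*

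**What the plan says.** Protocol section 7.1, criterion [7], sets the bone marrow reserve requirements, among them "hemoglobin $\geq 9 \text{ g/dL}$ (6.21 mmol/L". The mmol/L figure is given in parentheses as the equivalent of the g/dL figure, under the same inequality.

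A later bullet of the same criterion deals with transfusion: "Eligibility for hemoglobin may be reached by transfusion". It continues in g/dL only. "Patients with hemoglobin $> 8 \text{ g/dL}$ but $< 9 \text{ g/dL}$ may receive erythrocyte transfusions" defines who may be transfused, and treatment may start only some days later and "after the confirmation of hemoglobin level $\geq 9 \text{ g/dL". The 9 g/dL figure thus appears four times in the criterion and 6.21 mmol/L once.

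A note at the end of the criterion allows some tolerance: "Small changes from the outlined laboratory values, which are a result of biological or laboratory equipment variability" are accepted if they are isolated, transient and not a sign of a medical condition.

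On how the limit is applied, Protocol section 10.4.1 says "Patients may be enrolled on local laboratory values only". SAP section 6.15 lists as a protocol violation "Not meeting protocol inclusion/exclusion criteria [2], [3], [5] to [9], [11], [13] to [17]", a range that includes [7]. SAP section 6.13.4 has laboratory results listed "using SI units [International System of Units], when available".

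**The concern.** An eligibility limit printed in two units should classify every patient the same way in both. Here 6.21 mmol/L looks like the conversion of 10 g/dL, not of 9 g/dL. If so, the protocol holds two entry limits, and the unit on the laboratory report decides which one is applied.

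Three things depend on the figure. The first is who is eligible in a multicenter global trial where local values can decide enrollment. The second is the handling under Protocol section 7.3.1, which asks that entry criteria be followed explicitly and requires documented sponsor approval for a patient enrolled without meeting them. The third is the SAP section 6.15 list, which is built partly by programming. At 9.5 g/dL, the two figures give opposite answers to whether the patient met the criterion.

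**Working it through.** **Inputs from the documents** (Protocol section 7.1, criterion [7]): limit 9 g/dL; printed equivalent 6.21 mmol/L; transfusion band above 8 and below 9 g/dL.

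**Assumed input.** The documents state no conversion factor. Hemoglobin is reported in mmol/L either per monomer (about 16,114.5 g/mol; 16,000 to 16,125 taken as the range) or per tetramer (about 64,458 g/mol).

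**Formula.** mmol/L = (g/dL × 10) ÷ molar mass × 1000. For 16,114.5 g/mol the factor is 10 ÷ 16,114.5 × 1000 = 0.6206 mmol/L per g/dL.

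**Attempt to reproduce the printed figure.**

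| Convention | Molar mass (g/mol) | Factor | 9 g/dL in mmol/L | 6.21 mmol/L in g/dL |
|---|---|---|---|---|
| Monomer | 16,000 | 0.6250 | 5.63 | 9.94 |
| Monomer | 16,114.5 | 0.6206 | 5.59 | 10.01 |
| Monomer | 16,125 | 0.6202 | 5.58 | 10.01 |
| Monomer, loose upper bound | 17,000 | 0.5882 | 5.29 | 10.56 |
| Tetramer | 64,458 | 0.1551 | 1.40 | 40.03 |

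No row turns 9 g/dL into 6.21 mmol/L. Working backwards, that would need a molar mass of 90 ÷ 6.21 × 1000 = 14,493 g/mol, which fits neither form. By contrast, 10 × 0.6206 = 6.206, which rounds to 6.21. Rounding of the factor does not explain the gap: 0.62 and 0.621 give 5.58 and 5.59 mmol/L for 9 g/dL.

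**Size of the gap.** 6.21 − 5.59 = 0.62 mmol/L. In g/dL, 10.01 − 9 is about 1. Relative to the g/dL limit, 0.62 ÷ 5.59 = 11%.

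**Who falls in between.** A patient from 9.0 to just under 10.0 g/dL (about 5.59 to 6.20 mmol/L) passes on the g/dL figure and fails on the mmol/L figure.

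**Does other text close the gap?** The transfusion band, above 8 and below 9 g/dL, is about 4.96 to 5.59 mmol/L (8 × 0.6206 = 4.96). It stops where the disputed band begins, so a patient who fails only the mmol/L figure has no written transfusion route. The tolerance note covers isolated, transient variation, not a fixed difference between two printed limits.

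**The case against.** The arithmetic is hard to dispute; the consequences are easy to overstate. Most of the case against concerns them, and most of it stands.

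- **Sites.** A reader might infer that some sites did apply a different limit. No section says that any site reports hemoglobin in mmol/L. Protocol section 10.4.1 and Attachment 2 send hematology to a central laboratory, and the Attachment 2 footnote permitting local values is not the one attached to hematology. A site working in mmol/L would also have to convert to use the transfusion bullet, and might notice the mismatch. Even so, section 10.4.1 permits enrollment on local values right after describing routine tests, so a different limit remains possible.
- **Violation check.** A reader might infer that the SAP will flag everyone in the 9.0 to 9.99 g/dL band. SAP section 6.15 gives no coded value or unit. The SI wording in section 6.13.4 governs listings, and only when SI units are available. Such flagging would occur only if the check were coded from the mmol/L figure.
- **Exclusion subanalysis.** A flag does not automatically move a patient into it. SAP section 6.5 keeps treated patients who failed entry criteria in the main efficacy and safety analyses. Section 6.10.4 ties the subanalysis to patients enrolled inadvertently and kept on with sponsor approval, and to patients treated beyond progression. Section 6.15 narrows the reported violations to important ones.
- **Which figure is right.** Repeated use of 9 g/dL makes it tempting to call 6.21 a slip. The documents do not say so, and this review does not choose.
- **Timing.** Amendment (a) was approved in March 2015, after the planned last visit of August 2014, and is aimed at remaining patients. Little screening may have been left, although the documents do not say that enrollment had closed.

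None of this makes the two figures equal.

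**Conclusion.** Wrong as written, and minor. Criterion [7] prints one limit as two thresholds about 0.62 mmol/L (1 g/dL, 11%) apart, and nothing else in the protocol or SAP reconciles them. The result rests on one outside input, the molar mass of hemoglobin, and holds over every value tried.

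The possible effects are limited to eligibility decisions at any site reading the mmol/L figure and to violation flagging if that figure is coded. Both are conditional. The number of patients affected cannot be estimated, because the documents give no hemoglobin distribution and no reporting units by site. The primary overall survival analysis, the sample size and the error rates are untouched.

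**What to change.** The sponsor should state which hemoglobin limit is intended. The g/dL and mmol/L figures in criterion [7] should then be reconciled to that single threshold, with the conversion convention named. The transfusion bullet should be checked against it, so that its band and confirmation level meet the entry limit without a gap. The programmed check of criterion [7] under SAP section 6.15 should use the same value and name its unit.

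If patients have already been screened, a short query of recorded hemoglobin values between the two limits would show whether anyone was classified differently.

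The cost is small: correcting the figures in one criterion, fixing the matching constant in the violation program and, if wanted, one data query.

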7.2. Exclusion Criteria

Patients will be excluded from entering or enrolling in the study if they meet **any** of the following criteria:

- [11] Are currently enrolled in, or discontinued within the last 30 days from, a clinical trial involving an investigational product (including vascular endothelial growth factor receptor [VEGF-R] inhibitors) or non-approved use of a drug or device (other than the study drug/device used in this study), or concurrently enrolled in any other type of medical research judged not to be scientifically or medically compatible with this study.
- [12] Have previously completed or withdrawn from this study or any other study investigating LY2157299.
- [13] Have moderate or severe cardiac disease:
 - a) Have the presence of cardiac disease, including a myocardial infarction within 6 months prior to study entry, unstable angina pectoris, New York Heart Association (NYHA) Class III/IV congestive heart failure, or uncontrolled hypertension.
 - b) Have documented major electrocardiogram (ECG) abnormalities which are not controlled by medical treatments, for example, symptomatic or sustained atrial or ventricular arrhythmias, second- or third-degree atrioventricular block, bundle branch blocks, ventricular hypertrophy, or recent myocardial infarction.
 - c) Have major abnormalities documented by ECHO with Doppler (for example, moderate or severe heart valve function defect and/or left ventricular ejection fraction [LVEF] <50%, evaluation based on the institutional lower limit of normal). For additional details, refer to ECHO protocol ([Attachment 6](#)).
 - d) Have predisposing conditions that are consistent with development of aneurysms of the ascending aorta or aortic stress (for example, family history of aneurysms, Marfan-Syndrome, bicuspid aortic valve, evidence of damage to the large vessels of the heart documented by chest computed tomography [CT] scan with contrast).
- [14] Received prior nitrosourea (including lomustine or Gliadel®/local carmustine) therapy.
- [15] Received prior bevacizumab as part of a first-line treatment for GB (if treatment was concluded 12 months prior to enrollment, the patient may be eligible to participate in the trial).
- [16] Have a serious concomitant systemic disorder (for example, active infection including human immunodeficiency virus [HIV]) that, in the opinion of the investigator, would compromise the patient's ability to adhere to the protocol.
- [17] Have current acute or chronic myelogenous leukemia.

[18] Have a second primary malignancy that, in the judgment of the investigator and sponsor, may affect the interpretation of results (eg, slowly progressing tumors that in the past 3 years have shown an accelerated growth and are resistant to other treatments; for breast and prostate cancer patients see inclusion criterion [6]).

[19] Are pregnant or breast-feeding women.

[20] Are unwilling or unable to participate in the study.

7.3. Discontinuations

7.3.1. Discontinuation of Patients

The criteria for enrollment must be followed explicitly.

If a patient who does not meet enrollment criteria is inadvertently enrolled, Lilly or its designee must be contacted. In these cases, the investigator must obtain documented approval from Lilly to allow the patient to continue in the study enrollment or receive study drug (see additional guidance below).

Patients may be discontinued from the study or study drug treatment in the following circumstances to ensure their safety and to maintain the scientific integrity of the study:

- If Exclusion Criterion [13], [14], [15], [16], [17], [18], [19], or [20] is known after enrollment.
- Cases of pregnancy or failure to use adequate birth control (for women of reproductive potential) as outlined in [8] and [20]
- Enrollment in any other clinical trial involving an investigational product or enrollment in any other type of medical research judged not to be scientifically or medically compatible with this study.
- Investigator/Physician Decision
 - The investigator/physician decides that the patient should be withdrawn from the study or study drug.
 - If the patient, for any reason, requires treatment with another therapeutic agent that has been demonstrated to be effective for treatment of the study indication, discontinuation from the study drug occurs prior to introduction of the new agent.
- Patient Decision
 - The patient requests to be withdrawn from the study or study drug.
- Sponsor Decision
 - The investigator or Lilly stops the study or stops the patient's participation in the study for medical, safety, regulatory, or other reasons consistent with applicable laws, regulations, and good clinical practice.
- The patient is significantly noncompliant with study procedures and/or treatment.

Exceptions will be granted in rare circumstances, because GB patients have a serious or life-threatening condition for which there is no effective alternative therapy. In such cases, the investigator has to provide information on the patient's anticipated benefit or current benefit

from being entered in the study or receiving study drug. In these rare cases, the investigator must obtain documented approval from Lilly to allow the patient to continue in the study and/or receive study drug.

For cases involving continued treatment after objective disease progression (excluding cases in which pseudoprogression is assumed), the investigator needs to discontinue the patient as soon as he/she is made aware of this situation, but the patient will be followed until study objectives are met.

The reason and date for discontinuation from both study treatment and study itself will be collected for all patients. All patients enrolled will have procedures performed as shown in the Study Schedule ([Attachment 1](#)).

